### 3. Experimental plan

#### 3.1 Study design

This will be a prospective, Interventional, multicenter, open-label, uncontrolled phase I/II trial. 87 (18 phase I and 69 phase II including 6 patients treated at the RP2D during the phase I) patients will be included in several centers.

## Phase I

DLT monitoring must be performed during the first three cycles of treatment. Patients will be treated until disease progression.

In case of patient withdrawal before completing the entire third cycle for reasons other than DLT, a new patient will be included at this dose level.

The phase I part of this study will be designed as a standard 3+3 design for dose escalation/de-escalation and 3 to 6 patients will be enrolled in each cohort sequentially, depending on occurrence of dose limiting toxicities (Figure 1).

A standard 3 + 3 design will be followed in the dose escalation part of study.

Three dose levels for Irinotecan/Regorafenib (IRI 150/REGO 120, IRI 180/REGO 120, IRI 180/REGO 160) are planned as well as a -1 level (IRI 150/REGO 80) to be opened in case of maximum tolerated dose (MTD) was reached at level 1 (Table 1).

Table 1 :

Steps	Dose Levels	Number of patients
DL-1	IRI 150/REGO 80	0-6
DL1	IRI 150/REGO 120	3-6
DL2	IRI 180/REGO 120	3-6
DL3	IRI 180/REGO 160	3-6

At each dose level, three patients will be included. Three additional patients will be enrolled at the same dose level if one dose limiting toxicity (DLT) is observed in the first three patients of this dose level (Figure 1).

Figure 1 :

[figure not shown]

Table 2 : Dose escalation rules

Outcome (# DLT / # Patients)	Action
0 DLT out of the first 3 patients	Include 3 patients at the next dose level
1 DLT out of 3 patients	Include 3 additional patients at the same dose level.
$\geq 2$ DLT out of 3 patients	Stop dose escalation. Include 3 additional patients at the previous dose level (unless 6 subjects were already treated).
$\geq 2$ DLT out of 6 patients	Stop dose escalation. Include 3 additional patients at the previous dose level (unless 6 patients were already treated).

The MTD is defined as the dose at which at least two out of three to six patients experienced a DLT during the first three cycles of treatment.

Dose escalation will be stopped if MTD is reached or the last dose level (IRI 180/REGO 160) is reached (MTD not reached).

The recommended phase II dose (RP2D) is defined as the dose closest to the MTD at which a DLT is observed in 0/3 or 1/6 patients.

Should any patient discontinue the study prior to completing the entire (3 cycles) for reasons other than a DLT then a replacement patient will be added at that dose level.

### **DLT recording and assessment**

- Study sites will document any DLT immediately and report a DLT event to the Sponsor within 24 hours of site's awareness.
- Once recruitment of 3 or 6 patients per dose level has been completed, recruitment will be halted by default until the 3-cycle dose-finding treatment has been completed for each patient and sites have reported all relevant safety findings.
- The decision to stop, modify or continue escalation will be made by the project team (coordinator, statistician, project manager, safety vigilance head and vigilance manager) if there are no SUSARs. In the event of SUSARs, we will refer the matter to the independent scientific committee.
- The Sponsor will communicate further dosage information (dose escalation or de-escalation) and additional safety measures to all participating sites/investigators.

### **Phase II :**

The 6 patients treated at the RP2D in the phase I part will be included in the phase II part. The multicenter, phase II trial is planned to enroll 69 patients. The patients who meet the study eligibility criteria will be included to receive the study drug.

- ❖ **First inclusion:** april 2019
- ❖ **Inclusion period:** 12 months Phase I + 12 months Phase II
- ❖ **End of the inclusion period:** march 2021
- ❖ **Expected end of study:** june 2022
- ❖ **Report:** september-december 2022
- ❖ **Poster/public:** phase I (2020), phase II (april 2023 and july 2023)

### **3.2 Study period**

### **3.3 Compensation modalities**

The sponsor maintains clinical trial insurance coverage for this study in accordance with the laws and regulations of the country in which the study is performed.

## 4. Population

### 4.1 Number of planned patients

-87 patients included out of approximately 174 screened patients.

### 4.2 Inclusion criteria

#### Eligibility criteria for prescreening

The following criteria must be met at the time of prescreening:

1. Written informed consent for prescreening.
2. Prescreening of patients will be performed at the investigators' discretion up to a maximum of 21 days prior to full study screening. Investigators should ensure all patients will be eligible in terms of disease status within this timeframe.
3. Age  $\geq 18$  years.
4. Histological documentation of adenocarcinoma of the colon or rectum.
5. Synchronous or metachronous metastatic colorectal cancer not amenable to surgical resection with curative intent.
6. No prior therapy for metastatic disease.
7. Eastern Cooperative Oncology Group (ECOG) performance status  $\leq 1$ .
8. Life expectancy of at least 3 months.

Besides these basic criteria, any criterion as outlined below under inclusion eligibility criteria for full study and exclusion criteria, already known to prohibit the patient's participation in the study should be considered. No study-related procedures will be performed that are not covered by the prescreening informed consent form.

#### Eligibility criteria for full study

1. Written informed consent for full study
2. Documentation of tumor RAS mutation, wild-type homozygous, heterozygous status of UGT1A1 gene. The status of UGT1A1 gene will be performed by the laboratory chosen by the investigator (for information, appendix 1).
3. Serum uracile  $< 16$  ng/ml
4. Measurable disease, defined as at least one unidimensional measurable lesion on a CT scan, according to RECIST version 1.1.
5. ECOG performance status  $\leq 1$ .
6. Life expectancy of at least 3 months.

7. Adequate bone marrow, renal and liver functions as evidenced by the following laboratory requirements within 7 days prior to study treatment initiation:
  - a. Absolute neutrophil count (ANC)  $\geq 1\ 500/\text{mm}^3$  without biologic response modifiers such as granulocyte colony-stimulating factor (G-CSF), within 21 days before the start of study treatment,
  - b. Platelet count  $\geq 100\ 000/\text{mm}^3$ , without platelet transfusion within 21 days before the start of study treatment,
  - c. Hemoglobin (Hb)  $\geq 9\text{ g/dL}$ , without blood transfusion or erythropoietin within 21 days before the start of study treatment,
  - d. Serum creatinine  $\leq 1.5 \times$  upper limit of normal (ULN),
  - e. Serum calcium  $\geq \text{LLN}$  and  $\leq 1.2 \times \text{UNL}$  ; Serum magnesium  $\geq \text{LLN}$  and  $\leq 1.2 \times \text{UNL}$  ; Kalemia  $\geq \text{LLN}$ ,
  - f. Glomerular filtration rate as assessed by the estimated glomerular filtration rate (eGFR)  $\geq 50\text{ mL/min per }1.73\text{ m}^2$  calculated by the Modification of Diet in Renal Disease (MDRD) abbreviated formula,
  - g. Total bilirubin  $\leq 1.5 \times \text{ULN}$ ,
  - h. Alanine aminotransferase (ALT) and aspartate aminotransferase (AST)  $\leq 2.5 \times \text{ULN}$  ( $\leq 5 \times \text{ULN}$  for patients with liver involvement of their cancer),
  - i. Alkaline phosphatase (ALP)  $\leq 2.5 \times \text{ULN}$  ( $\leq 5.0 \times \text{ULN}$  for patients with liver involvement for their cancer and/or bone metastases).
8. Lipase  $\leq 1.5 \times \text{ULN}$ .
9. Adequate coagulation, as assessed by the following laboratory test results:
  - c. International normalized ratio (INR)  $\leq 1.5$  or prothrombin time (PT)  $\leq 1.5 \times \text{ULN}$ ,
  - d. Partial thromboplastin time (PTT) or activated PTT (aPTT)  $\leq 1.5 \times \text{ULN}$ ,

Note: Patients on stable dose (dose has not been changed in at least 28 days) of anticoagulation therapy will be allowed to participate if they have no sign of bleeding or clotting and INR / PT and PTT / aPTT test results are compatible with the acceptable benefit-risk ratio at the investigator's discretion. In such case, limits as noted would not apply.
10. For women of reproductive potential, negative serum beta human chorionic gonadotropin ( $\beta$ -HCG) pregnancy test obtained within 7 days before the start of study treatment.

Women not of reproductive potential are female patients who are postmenopausal or permanently sterilized (e.g., tubal occlusion, hysterectomy, bilateral salpingectomy).

11. For women of childbearing potential and men, agreement to use an adequate contraception for the duration of study participation and up to 4 months following completion of therapy for women and 6 months for male patients. Females of childbearing potential who are sexually active with a non-sterilized male partner must use 2 methods of effective contraception. The investigator or a designated associate is requested to advise the patient on how to achieve an adequate birth control. Adequate contraception is defined in the study as any medically recommended method (or combination of methods) as per standard of care.
12. Willingness and ability to comply with scheduled visits, treatment plan, laboratory tests and other study procedures.
13. Affiliation to the Social Security System.

#### 4.3 Non-inclusion criteria

1. Previous or concurrent cancer that is distinct in primary site or histology from colorectal cancer within 5 years prior to study inclusion, except for curatively treated cervical cancer in situ, non-melanoma skin cancer and superficial bladder tumors [Ta (non invasive tumor), Tis (carcinoma in situ) and T1 (lamina propria invasion)].
2. Discovery of metastases within 6 months after the termination of adjuvant chemotherapy.
3. Previous treatment for metastatic disease.
4. Radiotherapy within 28 days prior to first dose of treatment.
5. Active cardiac disease including any of the following:
  - a. Congestive heart failure  $\geq$  New York Heart Association (NYHA) class 2 (appendix 3),
  - b. Unstable angina (angina symptoms at rest), new-onset angina (begun within the last 3 months),
  - c. Myocardial infarction less than 6 months before first dose of treatment,
  - d. Cardiac arrhythmias requiring anti-arrhythmic therapy (beta blockers or digoxin are permitted).
6. ECG with a QT/QTc interval higher than 450 ms for men and higher than 470 ms for women.

7. Uncontrolled hypertension. (Systolic blood pressure > 140 mmHg or diastolic pressure > 90 mmHg despite optimal medical management).
8. Arterial or venous thrombotic or embolic events such as cerebrovascular accident (including transient ischemic attacks), deep vein thrombosis or pulmonary embolism within 6 months before start of treatment.
9. Persistent proteinuria of National Cancer Institute Common Terminology Criteria for Adverse Events (NCI-CTCAE V5) grade 3 (i.e. urinary protein  $\geq 3.5$  g/24 hrs)
10. Peripheral neuropathy > grade1 (NCI-CTCAE v5).
11. Major surgical procedure, open biopsy, or significant traumatic injury within 28 days prior to first dose of treatment.
12. Ongoing infection > grade 2 (NCI-CTCAE v5).
13. Known history of human immunodeficiency virus (HIV) infection.
14. Chronic hepatitis B or C infection (if hepatitis status cannot be obtained from medical records, re-testing is required).
15. Seizure disorder requiring medication.
16. Symptomatic metastatic brain or meningeal tumors.
17. Evidence or history of any grade 3-4 bleeding diathesis. Any hemorrhage or bleeding event  $\geq$  Grade 3 (NCI-CTCAE v5) within 4 weeks prior to the start of study medication.
18. History of organ allograft.
19. Non-healing wound, ulcer, or bone fracture.
20. Dehydration Grade  $\geq 1$  (NCI-CTCAE v5).
21. Substance abuse, medical, psychological, or social conditions that may interfere with the patient's participation in the study or evaluation of the study results.
22. Known hypersensitivity to any of the study drugs, study drug classes, or any constituent of the products.
23. Interstitial lung disease with ongoing signs and symptoms.
24. Concomitant intake of St. John's wort.
25. Live attenuated vaccines are prohibited 10 days before the treatment, during the treatment and 3 months after the termination of treatment
26. History of gastrointestinal fistula or perforation
27. Inability to swallow oral medication.
28. Any malabsorption condition.
29. Pregnant or breast-feeding subjects.

30. Any condition that, in the opinion of the investigator, would interfere with the evaluation of study treatment or interpretation of patient safety or study results.
31. Participation in another clinical study with an investigational product during the last 30 days before inclusion.
32. Patients who might be interconnected with or dependent on the sponsor site or the investigator.
33. Legal incapacity or limited legal capacity.

#### 4.4 Procedure

Before the inclusion of the patient in the study, the investigator must verify :

- that the screening inclusion and non-inclusion criteria have been met
- that the molecular test consent has been obtained.

**There's no paper form for this step and no registering.**

Inclusion:

The inclusion request will be performed **by fax for phase I**. After the consent form has been signed and all inclusion/ non-inclusion criteria have been met, the investigator will proceed with the inclusion through the paper inclusion form. It will be send by fax to the biostatistics unit [name] and project manager [name].

In the absence of a request for derogation, the biostatistics unit will return by fax the response to the investigator with the inclusion number and the dose level of the patient.

Then the CRA will **immediately fill out the data in the e-CRF** via

<https://ecrfcval.icm.unicancer.fr/CSOnline/> in order that an automatic reply can be sent by e-mail to confirm the success of the inclusion procedure to the:

- Representative of Sponsor – project manager,
- Investigator,
- Data manager,
- Statistician,
- Pharmacist

Once the patient is registered, he/she is considered to be enrolled in the study.

### 5. Visit Schedule

#### 5.1 Tabulated overview

Tabulated overview Folfirinox-R - Phase I/II	Screening		Treatment						Evaluation (Every 8 weeks)	End of treatment	Safety Follow-up	Follow-up	End of study
	D-21	D-7	Cycle 1		Cycle 2		Cycle 3		≥Cycle 4				
Cycles		C1D1	C1D8	C2D1	C2D8	C3D1	C3D8	≥C4					
Baseline documentation													
Informed consents 	X												
Demographics	X												
Complete medical history	X												
Eligibility Criteria checked 	X	X											
Physical examination 	X	X	X		X		X		X	X	X	X	
β-HCG blood test 			X										
Laboratory Studies													
12-lead ECG 	X		X 		X		X		X		X		
Complete blood count		X	X 	X	X	X	X	X			X		
Coagulation		X	X 		X		X		X		X		
Electrolyte panel		X	X 		X		X		X		X		
Chemistry panel 		X	X 	X	X	X	X	X			X		
Liver function test 		X	X 	X	X	X	X	X			X		
Tumor markers (ACE and CA 19-9)		X								X	X	X	

Tabulated overview Folfirinox-R - Phase I/II	Screening		Treatment						Evaluation (Every 8 weeks)	End of treatment	Safety Follow-up	Follow-up	End of study	
	D-21	D-7	Cycle 1		Cycle 2		Cycle 3		≥Cycle 4					
	Cycles		C1D1	C1D8	C2D1	C2D8	C3D1	C3D8	≥C4					
Urinary analysis 		X	X		X		X		X		X			
cfDNA analysis for RAS, UGT1A1 and serum uracil for evaluating DPD	X													
Imaging assessments														
Radiologic Tumor assessment 	X									X 	X 	X 		
Other Clinical Assessments														
DLT assessment 					X		X		X					
ECOG		X	X		X		X		X		X			
Body weight, BSA, height 		X	X		X		X		X	X	X			
Blood pressure 		X	X		X		X				X	X		
Concomitant medications		X	X		X		X		X		X	X		
Adverse events 		X	X		X		X		X		X	X	X 	
Drug dispensing			X		X		X							
Drug accountability					X		X		X		X			
Post-study survival status											X	X		
Anti-cancer medications											X	X		
Patient's diary checking 					X		X		X		X			
Ancillary studies														
EDTA tubes (3 X 7 ml) cfDNA 		X								X	X			
Paraffin block for analysis of DDR1 														X

Written informed consent will be obtained for pre-screening and for full study

Eligibility criteria will be checked for pre-screening and for full study

Including skin assessment for toxicities

Pre-menopausal women of childbearing potential only

12-lead ECG will be performed before and after the administration of Oxaliplatin during the three first cycles (Phase I and II) beyond cycle 3, ECG will be performed before administration of oxaliplatin

Includes: albumin, creatinine, creatinine clearance calculated according MDRD, lipase, glucose, TSH (every 6 weeks of CXD1), , total protein and uric acid

Liver function tests will be performed weekly during the three first cycles of treatment

Not required at day 1 of cycle 1 if those were completed within 7 days

Dipstick assessment with pH, protein, glucose, bilirubin, ketones, blood cells and leucocytes

CT scan of the abdomen, pelvis and chest or if the patient is allergic to iodine contrast agents, hepatic MRI and CT scan of the pelvis and chest without injection; RECIST criteria version 1.1

CT-Scans will be performed every 8 weeks

If the last radiological tumor assessment > 1 month

CT-Scan of safety follow-up will be performed if only it weren't done at the EOT visit

Period for DLT assessment is the three first cycles (only Phase I)

Height only at screening

Blood pressure will be monitored every other week during the first 3 cycles of treatment

Continuously from screening until FU visit, 30 days after last administration of study drug

A treatment diary will be handed over to patient on cycle 1 day 1

Three EDTA tubes will be collected at baseline, every 8 weeks during treatment and at the end of treatment

Paraffin-embedded human solid tissue blocks will be sent off at room temperature at the end of the enrollments

Only for unstabilized adverse events since the end of treatment

## 5.2 Screening period

Enrollment into FOLFIRINOX-R will be performed in two stages with two separate informed consent forms. Initially, all potential patients will consent to undergo molecular testing.

Molecular testing :

Only patients with RAS mutated tumor status, wild-type homozygous status of DPD and wild-type homozygous, heterozygous status of UGT1A1 will be screened for the study treatment.

**Each centre will choose its DPD and UGT1A1 genotyping laboratory. For your information a list is provided by the sponsor (cf appendix 1). The sponsor will bear the cost of the genotyping analysis (we draw your attention to the analysis of phenotyping which will not be reimbursed by the sponsor).**

A second consent form to screen for the clinical study (Clinical Trial Consent).

Both consent processes are independent of each other.

The following procedures and assessments will be performed **around 21 days of starting study Drug :**

- Obtainment of two informed consents
- A blood sample will be collected then will be shipped to laboratory that you will have chosen. To determine the DPD and UGT1A1 status (cf appendix 1). Check with the laboratory for the number, type and volume of blood tubes
- Documentation of RAS mutation
- Eligibility criteria checked
- Physical examination including review of all organ systems, examination of pertinent organ systems).
- Radiological tumor assessment using the RECIST criteria, version 1.1 (see appendix 4) must be performed. (CT scan of the abdomen, pelvis and chest or hepatic MRI and CT scan of the pelvis and chest without injection).  
A PET scan is not acceptable for radiological evaluation
- All additional suspected sites of disease should be imaged. An appropriate radiological evaluation should be obtained if bone metastases are suspected (e.g., bone scan)
- 12-lead ECG
- Complete medical history including demographics, allergies, prior surgery and prior chemo/radiation therapy with documentation of treatment response. See section XX for detailed instructions on the differentiation between medical history and adverse events

The following procedures and assessments will be performed **within 7 days of starting study drug:**

- Eligibility criteria checked
- ECOG performance status (appendix 5)
- Adverse events
- Physical examination including review of all organ systems, examination of pertinent organ systems, weight, BSA and height.
- A CBC with differential should be performed: RBC, hemoglobin, hematocrit, platelet count and WBC. WBC must include differential neutrophil, lymphocyte, monocyte, basophil and eosinophil counts
- Coagulation panel: Prothrombin time (PT) or the International Ratio of PT (PT-INR) and Partial Thromboplastin Time (PTT)
- Electrolyte panel: sodium, potassium, calcium, magnesium, chloride, phosphate, bicarbonate
- Chemistry panel : albumin, lipase, glucose, serum creatinine, clearance calculated according MDRD, uric acid, , protein total, TSH
- Liver function test panel: Aspartate Amino-Transferase (AST), Alanine Amino-Transferase (ALT), bilirubin (total and direct), alkaline phosphatase, GGT, Lactic Dehydrogenase (LDH)
- Three 7-ml EDTA tubes for cfDNA (not supplied). After centrifugation, the plasma will be frozen at -80°C until shipment.
- Tumor markers : CEA (Carcino-Embryogenic Antigen), CA 19.9 (Carbohydrate Antigen 19-9)
- Urine analysis: PH, protein, glucose, bilirubin, ketones, blood cells and leukocytes
- The blood pressure must be monitored every other week for the three first cycles of study treatment.

The blood pressure will be recorded by the patient and entered onto his treatment diary. Blood pressure measurements will be performed in patients sitting for 5 minutes prior to the evaluation.

- A β-HCG dosage for women of childbearing potential. Post-menopausal women with no menses for at least 1 year or surgically sterilized women will not be required to undergo a pregnancy test.
- Record of all concomitant medications except Homeopathy. All medicines and significant non-drug therapies taken within 7 days before study treatment must be recorded in the e-CRF.

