	
considered. No study-related procedures will be performed that are not covered by the prescreening informed consent form.
 
Eligibility criteria for full study
 
Inclusion criteria
 
 
1. Written informed consent for full study.
 
2. Documentation of tumor RAS mutation, wild-type homozygous, heterozygous status of UGT1A1 gene. The status of UGT1A1 gene will be performed by the laboratory chosen by the investigator (for information, appendix 1).
 
3. Serum uracile < 16 ng/ml
 
4. Measurable disease, defined as at least one unidimensional measurable lesion on a CT scan, according to RECIST version 1.1.
 
5. ECOG performance status ≤1.
 
6. Life expectancy of at least 3 months.
 
7. Adequate bone marrow, renal and liver functions as evidenced by the following laboratory requirements within 7 days prior to study treatment initiation: 
 
a. Absolute neutrophil count (ANC) ≥ 1,500/ mm^3 without biologic response modifiers such as granulocyte colony-stimulating factor (G-CSF), within 21 days before the start of study treatment,
 
b. Platelet count ≥ 100 000/mm^3 , without platelet transfusion within 21 days before the start of study treatment,
 
c. Hemoglobin (Hb) ≥ 9 g/dL, without blood transfusion or erythropoietin, within 21 days before the start of study treatment,
 
d. Serum creatinine ≤ 1.5 x upper limit of normal(ULN)
 
e. Serum calcium ≥ LLN and ≤ 1.2 x UNL ; Serum magnesium ≥ LLN and ≤ 1.2 x UNL ; Kalemia ≥ LLN,
 
f. Glomerular filtration rate as assessed by the estimated glomerular filtration rate (eGFR) ≥ 50 mL/min per 1.73
 
 
 

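### Section 5.2 requires wild-type homozygous DPD before screening, but the eligibility lists and the schedule test DPD only by serum uracil, and nothing in the public text says that both apply

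*Combined protocol and SAP*

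**What the plan says.** **Section 5.2 (Screening period, Molecular testing)** sets a genotype condition for being screened for study treatment: "Only patients with RAS mutated tumor status, wild-type homozygous status of DPD and wild-type homozygous, heterozygous status of UGT1A1 will be screened". Each centre chooses its own DPD and UGT1A1 genotyping laboratory. The sponsor pays for genotyping, and sites are warned that phenotyping is not reimbursed. The procedures ask for a blood sample to establish DPD and UGT1A1 status. Uracil is not mentioned.

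**The eligibility lists** use a different test. Inclusion criterion 3, in both the synopsis and 4.2, is "Serum uracile" below 16 ng/ml. Criterion 2 of 4.2 covers the other two molecular conditions, "Documentation of tumor RAS mutation, wild-type homozygous, heterozygous status of UGT1A1 gene", and leaves DPD out. The prescreening list, introduced by "The following criteria must be met at the time of prescreening", has no DPD item.

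**Section 5.1** schedules serum uracil as the test for evaluating DPD, without a cut-off. It schedules no DPD genotyping.

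**Section 4.4** asks the investigator to verify the screening criteria and "that the molecular test consent has been obtained". It adds that there is "no paper form for this step and no registering". Inclusion then proceeds once consent is signed and "all inclusion/ non-inclusion criteria have been met".

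**The concern.** The protocol itself describes DPD, in 6.11, as the enzyme that breaks down fluorouracil. Section 6.1 gives every patient 5-FU at 400 mg/m² by bolus and then 2400 mg/m² over 46 hours. Only irinotecan and regorafenib vary by dose level, and the dose-modification rules in 6.6 contain no adjustment for DPD status. Screening is thus the point at which DPD status decides exposure to 5-FU.

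A site that works from the numbered criteria would find no bar to a variant carrier with acceptable uracil. A site that works from 5.2 would stop the same patient before screening. In a multicentre trial, the answer on a pre-treatment safety condition should not depend on which section a site reads.

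**Working it through.** No formula applies. The check compares every DPD statement in the text and then asks which patients the rules treat differently.

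**Step 1. Where each rule appears.**

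| Place | DPD genotype required | Serum uracil |
|---|---|---|
| Synopsis, inclusion criteria | no | yes, < 16 ng/ml |
| 4.2, prescreening (8 criteria) | no | no |
| 4.2, full study (13 criteria) | no | yes, < 16 ng/ml |
| 4.3, non-inclusion (33 criteria) | no | no |
| 5.1, schedule | no | yes, no cut-off |
| 5.2, Molecular testing | yes, wild-type homozygous | not named |

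Count for 4.2 and 4.3: 8 + 13 + 33 = 54 numbered criteria. A DPD genotype is named in 0 and serum uracil in 1. The synopsis has 8 + 13 + 32 = 53, with the same 0 and 1. Across the document, uracil is the DPD test in three places (with its cut-off in two) and the genotype condition stands in one.

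**Step 2. The four possible patients.**

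| DPD genotype | Uracil | 5.2 | Listed criterion 3 |
|---|---|---|---|
| wild-type homozygous | < 16 ng/ml | passes | met |
| wild-type homozygous | ≥ 16 ng/ml | passes | not met |
| variant carrier | < 16 ng/ml | stopped | met |
| variant carrier | ≥ 16 ng/ml | stopped | not met |

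The first and last rows give the same answer under either rule. In the second row the patient is excluded at inclusion, because 4.4 requires the listed criteria to be met. Only the third row depends on which section is followed.

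**Step 3. Does another provision settle the third row?**

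- Section 4.4 bases inclusion on the listed criteria, which omit the genotype. Its check on the molecular step names the consent but not the DPD result.
- Eligibility is checked twice under 5.1 and 5.2, and 5.3 requires it to be confirmed and documented. Those checks protect the uracil rule. They do not bring in a genotype rule that the lists lack.
- Non-inclusion criterion 30 of 4.3, "Any condition that, in the opinion of the investigator, would interfere with the evaluation of study treatment", could exclude the patient, but it is discretionary.
- Appendix 1 is described as a list of laboratories given for information. Its content and the inclusion form are not in the available text.

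**Step 4. Is uracil likely to be missed?** This is a minor operational risk. Section 5.2 omits uracil and declines to pay for phenotyping, but 5.1 schedules the test, and 5.3 requires screening assessments to be complete before enrolment.

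**The case against.** The strongest reply is that this is a condition left out of a list, not a contradiction. Section 5.2 describes two stages with separate consents. The genotype condition belongs to the first, and criterion 3 belongs to the full-study list that follows. A variant carrier stopped at stage one never reaches criterion 3, and no text says that meeting 4.2 overrides 5.2. The reimbursement sentence even suggests that phenotyping was expected alongside genotyping, and the blood-sample line names no method. For phase I, the inclusion form also goes to the biostatistics unit before a number is issued.

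Much of this stands. Applying both tests in sequence honours all the available text and is probably what was meant. But the protocol does not say so. Criterion 2 of 4.2 repeats the RAS and UGT1A1 conditions of 5.2 without the DPD one, so a reader could equally suppose that uracil had replaced genotype. Whether the inclusion form would catch such a patient cannot be seen.

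A reader might also infer statistical consequences, which the documents do not support:

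- **Per-protocol set.** Section 10.2 judges eligibility by major violations of the inclusion and exclusion criteria. The genotype is in neither list, so read literally the patient counts as eligible.
- **Primary endpoint.** Section 2.2.1 defines the phase II denominator as all treated patients.
- **Toxicity and recommended phase II dose.** The documents give no added risk for a variant carrier with uracil below 16 ng/ml, so no effect on either can be claimed.

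**Conclusion.** The point holds as an inconsistency that should be corrected. One current section imposes a DPD genotype condition that the eligibility lists and the schedule do not carry, and that section does not name the DPD test on which the lists rely. The practical consequence is confined to one type of patient, the DPD-variant carrier with uracil below 16 ng/ml, for whom sites could reach opposite decisions on full-dose 5-FU.

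The size is limited. Every reading leaves at least one DPD check before 5-FU, the number of such patients is unknown, and no sample size, error rate or power figure depends on the rule. It would go too far to say that the protocol leaves patients unscreened for DPD deficiency, or that the two rules cannot both be followed.

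The conclusion assumes that the unseen Appendix 1 and inclusion form do not state the combined rule. If they do, the remaining task is only to carry that rule into the protocol text.

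**What to change.** Require both tests, in the same words everywhere:

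- Add wild-type homozygous DPD genotype to the inclusion criteria in the synopsis and 4.2, and to the 5.1 schedule.
- Name serum uracil < 16 ng/ml in the 5.2 procedures.
- Add the DPD result to what 4.4 asks the investigator to verify, and check that the inclusion form records it.
- Keep the reimbursement sentence if that is the sponsor's policy, but state there that uracil is still required.

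If the sponsor has deliberately replaced genotype with uracil, it should say so and remove the 5.2 condition by amendment.

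The cost is wording in four places and one line in 4.4. The protocol already calls for both tests. Sites that now follow only the numbered criteria would have to add genotyping, for which 5.2 says the sponsor pays, and there may be a few more screening failures.
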